Specific Aim 1: To determine the feasibility of employing rapid cardiac risk stratification and psychological screening to identify patients with LRCP-A in the ED for subsequent referral to MBSR. Currently there are no tools regularly used in the ED to screen for LRCP-A, however, our *working hypothesis* is that evidence-based tools can be used to identify patients at risk for LRCP-A. To accomplish this, we will execute

[name]

a two-step prospective screening approach: 1. Determine score on the validated and widely used HEART scale [50, 51]. 2. Those with a HEART score <4 will complete the General Anxiety Disorder 7-item (GAD-7) questionnaire. Scores ≥ 10 are indicative of the criterion standard for moderate to severe symptoms of anxiety [52]. In this pilot study, feasibility will be assessed in a number of ways including the determination of the rate of eligible subjects per month, proportion of eligible subject who enroll, and proportion who complete the MBSR intervention. *Expected outcome:* This aim is designed to provide data regarding the feasibility of the risk stratification, psychological screening, and MBSR referral approach.

Specific Aim 2: To determine the effect of an MBSR training program for patients with LRCP-A on mental health (longitudinal GAD-7 scores, quality of life (PROMIS Global Short Form), and ED resource utilization (return ED visits). *Our working hypothesis* is that early referral to MBSR will help patients better regulate their thoughts, feelings, and bodily sensations related to their anxiety symptoms and have a significant positive effect on patient-centered outcomes such as mental health, quality of life as well as decreased ED resource utilization. To this end we will assign LRCP-A patients identified in SA1 to usual care referrals versus MBSR. We will then follow these patients for outcomes including change in GAD-7 scores, PROMIS Global Short Form, ED utilization among other outcomes at 6 weeks, 3 months, 6 months, and 1 year. *Impact:* This aim will establish a viable and novel treatment pathway for ED patients identified to be at risk for LRCP-A to ensure the possibility of early directed intervention.

3. Inclusion/Exclusion Criteria

Inclusion:

- Age: 18 through 70
- Chief complaint of chest pain
- HEART Score of 0-3 indicating Major Adverse Cardiac Events (MACE) risk equivalent to $\leq 2\%$
- GAD-7 score ≥ 10

Exclusion:

- Age <18 or ≥ 71
- Chief complaint of anxiety, panic, or similar

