8	The rest of your life: Making the practice your own	
 ▪ Body scan ▪ MM ▪ Sitting meditation 	
 ▪ Review of the course with an emphasis on daily strategies for maintaining and deepening mindfulness skills ▪ Sharing of participant perspectives on the program; welcoming all comments 	
 ▪ Mindfulness resources handout ▪ Continuing the practice & making it your own ▪ Bringing seamless attention to life

Outcome assessments: The schedule of assessments is shown in Table 2. These assessments will take place in the method most convenient for the patient (telephone, mail, or online REDCap survey completion). These are all methods the PI and his research team are currently using. **The primary outcome of interest will be the mean longitudinal change in GAD-7 scores between intervention groups at each time point.**

Domain	Measure	# of Items	Time Period Investigated				
			ED	45 day	3 mo	6mo	12mo
MACE [†] Risk	HEART Score	5	x				
ACS Risk	PreTest Consult ACS	8	x				
Demographics	Age, Race, Gender, Education etc.	10	x				
Medication Use	Standard Items	2	x	x	x	x	x
Medical Comorbidity	9-Condition Checklist	9	x				
Chest Pain Symptoms	Custom Items and Numeric Rating Scale	5	x				
Somatization	Patient Health Questionnaire (PHQ-15)	15	x	x	x	x	x
Anxiety Severity	Generalized Anxiety Disorder Scale (GAD-7)	7	x	x	x	x	x
Panic	PHQ Panic Scale	5	x	x	x	x	x
Social Anxiety	Mini-SPIN	3	x	x	x	x	x
PTSD	4-Item screen	4	x	x	x	x	x
Depression	Patient Health Questionnaire (PHQ-8)	8	x	x	x	x	x
Cardiac Anxiety	Cardiac Anxiety Questionnaire	18	x	x	x	x	x
Resilience	Brief Resilience Scale	6	x				
Pain Catastrophizing	Pain Catastrophizing Scale	13	x				
Healthcare Utilization (12 mo Pre-ED)	Custom Items	6	x				
Healthcare Utilization (Post-ED assessment)	Custom Items	6		x	x	x	x
Healthcare Related Quality of Life	PROMIS Global Short Form	10	x	x	x	x	x
Life Trauma	Traumatic Life Events Questionnaire	18	x				
MBSR Mechanism of Action	Cognitive and Affective Mindfulness Scale-Revised (CAMS-R)	10	x	x	x	x	x
MBSR Evaluation	Toronto Mindfulness Scale (TMS)	13	x	x	x	x	x

[†]Major Adverse Cardiac Event

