The goals are to collect preliminary data regarding the feasibility and effectiveness of the MBSR referral and approach compared with standard of care referral. Eligibility, recruitment, and retention information will be tabulated. Frequencies and percentages will be summarized by group for categorical variables, and continuous and count variables will be summarized by group using the mean, standard deviation, and range. The primary outcome of interest will be a comparison of the mean change in GAD-7 scores at 3 months using the t-test. Secondary analysis will look at the comparison of mean change in GAD-7 longitudinally using repeated measures ANOVA. The repeated measures ANOVA will compare scores between groups and compare scores over time within groups. Similar analyses will be used for the other efficacy outcomes. The proportion of subjects with a visit, time to first visit, and number of visits will be compared using chi-square, log-rank, and Wilcoxon rank sum tests, respectively. A 5% significance level will be used for all tests.

Because there is minimal published data to guide power calculations in this population for our outcome of interest we have chosen a sample size of 12 for each interventional arm in this pilot study on the basis of feasibility as described by Julious [62]. This sample size of 12 will be increased to 20 per arm to account for an

[name]

estimated 40% drop out rate prior to completion of the MBSR intervention. Thus, the total number of subjects we expect to enroll to the intervention is 40. All subject data will be analyzed on an intention to treat basis.

9. Privacy/Confidentiality Issues

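### Section 8 applies an unadjusted 5% level to roughly 7 to 23 between-arm tests in a feasibility-sized pilot and plans no confidence interval for any arm difference

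*Combined protocol and SAP*

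**What the plan says.** Section 8 (Statistical Considerations) sets the primary comparison: "The primary outcome of interest will be a comparison of the mean change in GAD-7 scores at 3 months using the t-test". It continues: "Secondary analysis will look at the comparison of mean change in GAD-7 longitudinally using repeated measures ANOVA". It then widens the plan: "Similar analyses will be used for the other efficacy outcomes", without listing those outcomes. Visits get three further procedures: "The proportion of subjects with a visit, time to first visit, and number of visits will be compared using chi-square, log-rank, and Wilcoxon rank sum". The paragraph ends: "A 5% significance level will be used for all tests".

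The section gives no multiplicity adjustment, no ordering of the secondary outcomes and no exploratory label. Results are to be summarized by group, as frequencies and percentages or as mean, standard deviation and range. Neither Section 8 nor any other part of the document mentions a confidence interval.

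On size, Section 8 says "we have chosen a sample size of 12 for each interventional arm in this pilot study on the basis of feasibility", because there is little published information on which to base power. The number is raised to 20 per arm for dropout. No effect size, standard deviation or power is stated.

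Two other places matter. Section 5, in the outcome assessments for Specific Aim 2, defines the primary outcome differently: "The primary outcome of interest will be the mean longitudinal change in GAD-7 scores between intervention groups at each time point". Section 2, Specific Aim 2, gives the working hypothesis that early referral will "have a significant positive effect on patient-centered outcomes such as mental health, quality of life as well as decreased ED resource utilization".

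**The concern.** One sentence makes a 5% threshold the only inferential rule for every comparison in a study that was not sized for hypothesis testing. This has two consequences. Across many unadjusted tests, some p-value below 0.05 can easily arise by chance, and Aim 2 is worded so that such a result on mental health, quality of life or ED use could be cited in its support. In the other direction, the single primary test has low power for moderate effects, so a p-value above 0.05 says little.

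A pilot can supply an estimated difference and its precision, which is what the planning of a later trial needs. The plan does not commit to reporting either for the contrast between arms.

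**Working it through.** **1. The plan's own figure.** Section 8 starts from 12 per arm and 40% dropout: 12 / (1 − 0.40) = 20 per arm, and 2 × 20 = 40 in total. This reproduces. Section 5 (feasibility outcomes) assumes 10% loss at each follow-up. The 3-month visit is the second, so 20 × 0.9² = 16.2, about 16 per arm. I use 12, 16 and 20 per arm as the range.

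**2. How many between-arm tests.** Table 2 repeats ten scales at baseline and all four follow-ups: PHQ-15, GAD-7, PHQ Panic, Mini-SPIN, the PTSD screen, PHQ-8, Cardiac Anxiety Questionnaire, PROMIS, CAMS-R and TMS. Section 8 implies two between-arm tests per efficacy scale (the 3-month t-test and the repeated measures comparison), plus three visit tests.

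- All ten scales: 10 × 2 + 3 = 23.
- Without CAMS-R and TMS, which Fidelity Monitoring (Section 5) uses to check receipt and use of the intervention: 8 × 2 + 3 = 19.
- Only the outcomes Aim 2 names (GAD-7, PROMIS, visits): 2 × 2 + 3 = 7.

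The count could exceed 23 if scales are tested at each time point or visits by type. The planned within-group comparisons over time are not counted.

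**3. Chance of a false positive.** Assume two-sided tests (the plan does not say) and no true difference. With k independent tests, the chance of at least one p<0.05 is 1 − 0.95^k in either direction, and 1 − 0.975^k in the direction of benefit.

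| k | Either direction | Benefit only |
|---|---|---|
| 7 | 30.2% | 16.2% |
| 19 | 62.3% | 38.2% |
| 23 | 69.3% | 44.1% |

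Independence is an upper case here, because the two tests on one scale share data and the scales overlap. Two simulations allow for this.

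- *Equal correlation among all test statistics.* For 23 tests at correlation 0.3, 0.5 and 0.7: 58%, 45% and 31% in either direction; about 30%, 22% and 15% for benefit. For 7 tests at 0.7: 18% and 9%.
- *Simulated trials* with 12 per arm, correlation of 0.6 over time within a person, and correlation of 0 to 0.7 between scales. For 23 tests: 61% to 41% in either direction, 37% to 22% for benefit. For 19 tests: 54% to 37%, and 31% to 19%. For 7 tests: about 23% to 25%, and 12% to 14%.

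Across both models and all counts, the range is about 18% to 61% in either direction and 9% to 37% for benefit.

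If the primary is read as in Section 5, at each of four follow-ups, the primary alone gives 1 − 0.95⁴ = 18.5% in either direction and 1 − 0.975⁴ = 9.6% for benefit, if independent.

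**4. Power and precision of the primary test.** Power uses the two-sided noncentral t with 2n − 2 degrees of freedom and noncentrality d√(n/2). The documents give no effect, so d (in SD units) is an assumption and is shown as a range. The 95% half-width is t × √(2/n): 2.074 × √(2/12) = 0.85, 2.042 × √(2/16) = 0.72 and 2.024 × √(2/20) = 0.64 SD.

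| n per arm | d=0.3 | d=0.5 | d=0.8 | d=1.0 | d for 50% power | d for 80% power | CI half-width |
|---|---|---|---|---|---|---|---|
| 12 | 10% | 22% | 47% | 65% | 0.84 | 1.20 | 0.85 SD |
| 16 | 13% | 28% | 59% | 78% | 0.72 | 1.02 | 0.72 SD |
| 20 | 15% | 34% | 69% | 87% | 0.64 | 0.91 | 0.64 SD |

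For an assumed SD of 4 to 6 GAD-7 points, the half-width is 3.4 to 5.1 points at 12 per arm and 2.6 to 3.8 points at 20 per arm, on a scale of 0 to 21.

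**The case against.** The strongest reply is that this is a declared pilot with one named primary test. Section 8 describes its goal as preliminary data and calls the longitudinal analysis secondary, so a careful reader would already discount the remaining p-values. That stands in part: the plan does have a primary, and the multiplicity falls mainly on what lies below it. It does not settle the matter, because Section 5 states a different primary and nothing labels the other tests exploratory.

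A second reply is that group means and SDs, with group sizes, let a reader work out the difference and its interval. That is true for continuous outcomes if change scores are summarized, which the plan does not specify. It does not serve the log-rank or Wilcoxon comparisons.

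The count is also open to challenge. A reader might take 23 as a minimum, but the plan never lists its efficacy outcomes. Two of the ten scales have a fidelity role. The visit measures overlap with Aim 1 feasibility measures, so their direction of benefit is not clear-cut. The range of 7 to 23 reflects this.

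Finally, a reader might infer that the trial's conclusion will rest on whichever test crosses 5%. No such decision rule is written. Aim 2 states a joint working hypothesis over several outcomes, and does not say that any one of them is enough.

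**Conclusion.** The point stands as an inexpensive improvement to the inferential rule and the reporting. On every count and correlation examined, the chance of some nominally significant result with no true effect is several times the 5% attached to each test.

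Two stronger conclusions are tempting and should not be drawn. A chance *benefit* is not likely in the sense of more probable than not: the 69% figure counts differences in either direction under independence, and the largest figure for benefit is 44%. Nor can one say that a real effect will usually be missed. That is so only if the true effect is below about 0.84, 0.72 or 0.64 SD at 12, 16 or 20 per arm, and the documents give no effect size to judge by. At an assumed 0.5 SD, the primary test would miss the effect in about two-thirds to four-fifths of trials.

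These figures assume two-sided tests, approximately normal statistics, the stated correlation models, and no arm difference arising from assignment by enrolment period.

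**What to change.** In Section 8, replace "A 5% significance level will be used for all tests" with:

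> The 5% level applies only to the primary comparison of GAD-7 change at 3 months. All arm comparisons, including the primary, will be reported as an estimated difference (or other effect measure suited to the outcome) with a 95% CI; all other comparisons are exploratory and will carry no statement of significance.

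Align the primary outcome in Section 5 (outcome assessments for Specific Aim 2) with the 3-month comparison in Section 8. Without this, the new sentence would refer to a primary that the protocol defines in two ways.

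In the Aim 2 working hypothesis (Section 2), delete the word *significant* and add that the pilot will estimate these effects.

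The cost is wording only, with no added patients, assessments or alpha correction. The sponsor gives up calling secondary outcomes statistically significant. The primary test keeps its low power for moderate effects, but the interval will show the reader how imprecise the estimate is.
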